Clinical Investigation Plan

CP357

Investigation of the clinical performance of Biatain Fiber Ag on burns

May 2023 – January 2024

ClinicalTrials.gov ID: NCT05824026

Approval date of version 3.0: 2023/06/20

This confidential document is the property of Coloplast A/S.
No unpublished information contained herein may be
disclosed without written approval of Coloplast A/S.

CHANGE LOG

VERSION NUMBER	ISSUED BY (INITIALS)	COMMENTS (MAJOR CHANGES SINCE LAST REVISION)
1.0	[REDACTED]	[REDACTED]
2.0	[REDACTED]	[REDACTED]
3.0	[REDACTED]	[REDACTED]

SYNOPSIS OF THE CLINICAL INVESTIGATION

Title and aim

Investigation of the clinical performance of Biatain Fiber Ag on burns.

The overall purpose of this investigation is to obtain clinical data supporting effectiveness of the final product to obtain the CE-mark.

Test product

The test product, Biatain Fiber Ag is a non-CE-marked gelling fiber wound dressing, containing silver. The product is intended for moist wound healing and exudate management of moderate to high exuding wounds. The product has a classification III, as it contains the active ingredient silver.

Intended use

Biatain Fiber Ag is **Primary** intended for moist wound healing and exudate management of moderate to high exuding wounds, including cavity wounds, that are infected or at risk of infection.

Objective

The primary objective is to evaluate the non-inferiority of Biatain Fiber Ag to similar products using percentage of wounds healed in partial thickness burns within 14 days.

Design of the investigation

The clinical investigation is a non-comparative, one-armed, open-labelled, multi-centre study.

The total study duration for the subject will be approximately two weeks, consisting of a two-week test period and 4 study visits (V0/V1, V2 and V3). V3 will also terminate the 2-week study period.

[figure not shown]
Expected duration of the clinical investigation

The expected duration of the clinical investigational period is approximately 14 days (+/-2 days).

Primary endpoint and Exploratory endpoints

Primary endpoint

Percentage of wounds healed within 14 days ($\geq 95\%$ reepithelialisation)

Additional assessments

- Use of antibiotics and antiseptic since last visit

Population/subjects

The clinical investigation will be conducted in a total of 50 eligible subjects with a partial thickness burn wound that are infected or at risk of infection. To be included in the investigation, the subjects must comply with the criteria presented below.

Inclusion criteria	Exclusion criteria
1. Has signed informed consent	1. Is pregnant/breastfeeding
2. Is between 18-65 years old (both included)	2. Is currently receiving or has within the past 60 days received radio- and/or chemotherapy (low doses radio- and/or chemotherapy is allowed for other indications than cancer if assessed by investigator not to influence study wound area)
3. Is capable of following study procedure (assessed by investigator).	3. Known history of skin sensitivity to any components of the test dressings
4. Has a partial thickness burn wound	4. >72 hours from time of injury
5. Has a burn wound that is infected or at risk of infection (assessed by investigator)	5. Intake of antibiotics within one week before the start of the enrolment
6. The size of burn (including both study wound and non-study injuries) has a Total Body Surface Area (TBSA) less than 10% (assessed by investigator).	6. Use of chemical debridement
7. The wound should fit under a 20x30 cm dressing (600 cm ²) or smaller	7. Participation in any other clinical studies that can compromise this study treatment (assessed by the investigator).
8. The shape and location of the wound should be suitable for photo capture (assessed by the investigator).	
9. Has a wound that has medium to high level of exudate (assessed by the investigator)	
10. Is suitable to use the test product for wound treatment (assessed by the investigator).	

LIST OF ABBREVIATIONS

ABBREVIATION	WRITTEN OUT	EXPLANATION
ADE	Adverse Device Effect	See section 18.2
AE	Adverse Event	See section 18.1
ASADE	Anticipated Serious Adverse Device Effect	See section 18.4.2
CA	Competent Authority	
CIP	Clinical Investigation Plan	
CRF	Case Report Form (paper or electronic)	Questionnaire to be used for data collection
CM	Clinical Manager	
DQF	Data Query Forms	A DQF is a query specifically used in clinical research. The DQF is the primary data query tool from the sponsor to clarify discrepancies and ask the investigator for clarification. The DQF is part of the data validation process in a clinical investigation.
DD	Device deficiency	
[REDACTED]	[REDACTED]	
EC	Ethics Committee	

1.2. Chief Investigator

CHIEF PRINCIPAL INVESTIGATOR

This clinical investigation involves up to 10 sites in United Kingdom (UK).

2. Rational/justification for conducting the clinical investigation

Gelling fibers are highly absorbent advanced wound dressings made to manage moderate to large amounts of exudate. They form a gel when in contact with the wound and thus conforms well to the wound bed. Gelling fibers are primary dressings and always require a secondary dressing to keep them in place.

The product features ensure absorption and exudate management while creating a moist wound healing environment for moist wound healing for a broad variety of acute and chronic wounds.

The major roles for antimicrobial dressings (such as silver dressings) are to reduce the bioburden in acute or chronic wounds that are at risk of infection, infected or prevented from healing due to microorganisms. Furthermore, the dressings can provide an antimicrobial barrier for acute or chronic wounds at high risk of infection or re-infection.

Biatain Fiber Ag is a class III device and clinical data on the actual product is required for the CE-mark.

Silver containing products has been on the market for decades and Silver containing gelling fibers similar to Biatain Fiber Ag has been on the marked for more than two decades. Biatain Fiber Ag is thus a well-known type of product and based on a well-established technology. The product is intended to be used by Health Care Professionals and the handling of the product is evaluated to be simple and well known as it is similar to other wound care dressings, and it is evaluated that most HCP would not require any extra training prior to the use of the product. It is therefore evaluated that the potential bias due to study inclusion is limited. A large portion of the clinical studies conducted and published previously on silver containing wound dressings is non-comparative. It is evaluated that it would not be ethical correct to perform a clinical study with a similar non-antimicrobial dressing and conducting a comparative study with a similar silver containing dressing as comparator would require a large amount of patients with no additional benefit for the patients included. The study design chosen has therefore been a non-comparative study, which has been evaluated to be sufficient, and the data obtained will be evaluated and compared to data on performance available on similar devices.

Several clinical investigations on silver containing gelling fibers have been published mainly in the chronic wound indication venous leg ulcers and the acute wound indication burns. The wound indication burns have therefore been chosen for the clinical study providing clinical data on an acute wound indication. The data obtained in the clinical investigation will in the Clinical Evaluation Report be evaluated and compared to the data available on similar devices to ensure the performance and safety profile for Biatain Fiber Ag is similar to other antimicrobial gelling fibers.

3. Objective of the clinical investigation

3.1. Primary Objective

The primary objective is to evaluate the non-inferiority of Biatain Fiber Ag to similar products using percentage of wounds healed in partial thickness burns within 14 days.

4. Investigational device

[figure not shown]
[figure not shown]
The investigational test product will be used according to intended use and indications during the investigation.

4.1. Description of investigational device

The investigational device, Biatain Fiber Ag is a non-CE-marked gelling fiber wound dressing, containing silver.

The product has a classification III, as it contains the active ingredient silver.

4.2. Manufacturing

Coloplast A/S, [REDACTED] is legal manufacturer of the medical device on the EU, UK and US market and has the overall responsibility for the design and documentation of the product. [REDACTED]

4.3. Identification and traceability of the investigational test product

The investigational test product will be identified as Biatain Fiber Ag and will in this investigation be available in size 20 x 30 cm. For smaller size wounds the dressing can be cut to fit the wound.

The investigational test product is labelled as per regulations and include "Exclusively for Clinical Investigational Use" on the label and accounted for through a master sponsor accountability log.

Upon Ethics Committee (EC) and Competent Authority (CA) approval, investigational test products will be shipped to the local Principal Investigator (PI), or delegate. Additionally, all investigational test products will be accounted for and documented on a site accountability log. All unused products will be returned to Coloplast at the completion of the investigation.

4.4. Intended use of the device in the clinical investigation

Biatain Fiber Ag is **Primary** intended for moist wound healing and exudate management of moderate to high exuding wounds, including cavity wounds, that are infected or at risk of infection.

See instruction for use (IFU) in Appendix 1.

4.5. Intended population for the device

Biatain Fiber Ag is intended to a wide range of moderate- to highly exuding wounds. This includes acute wounds such as donor sites, traumatic wounds, post-operative wounds, partial thickness wounds; and chronic wounds such as arterial- and venous ulcers, diabetic ulcers, pressure ulcers (stage II- IV), and exudate absorption in oncology wounds.

In this clinical investigation the intended population is subjects with **partial thickness burns**, that are infected or at risk of infection.

4.6. Handling of the investigational device

The handling of Biatain Fiber Ag is described in detail in the IFU, which is included in the box containing the test product. Storage conditions is also stated in the IFU.

Wear time

The dressing should be replaced when wound care practice indicates that a change is needed, or when it has reached its maximum absorption capacity, but no more than 7 days.

The test product can be covered by a moisture-retentive secondary dressing appropriate to the clinical condition of the wound and volume of exudate.

Removal

If removing the dressing is difficult, the dressing should be fully saturated with sterile saline or water and removed slowly.

All PI's and delegates will receive training by sponsor and/or PI in handling and correct use of the investigational test product.

For further details regarding Biatain Fiber Ag, please refer to the IFU in Appendix 1.

4.7. Total number of devices intended for the clinical investigation

The subjects will be included for 2 weeks of investigation. On average, it is expected that subjects will require 1-4 dressing changes/week. Therefore, each subject is expected to use a maximum of 8 products during their participation. Additionally, an extra buffer will be produced and in total 1000 dressings.

5. Design of the clinical investigation

5.1. General

The clinical investigation is a non-comparative, one-armed, open-labelled, multi-centre study. The study is planned to be conducted in UK.

The total study duration for the subject will be approximately two weeks, consisting of a two-week test period and 4 study visits (V0/V1, V2 and V3)

In total 50 subjects will be included in the investigation. Eligible subjects are invited to a Screening Visit (V0). Screening visit (V0) and Baseline visit (V1) can be combined and performed on the same day. If subject wishes to reconsider his/her participation at V0, the subjects must be given at least 24 hours to consider their participation. V0 can be done remotely.

At V0 the subject will be informed about the investigation, where the PI or delegate will give a detailed information about the requirements, the content and what it involves participating in the investigation. See section 6.2 for recruitment.

Informed Consent will be signed at the Baseline Visit (V1) and obtained before any study-related activities are initiated. Informed consent must be signed within 72 hours from burn injury.

Subjects will use the investigational test product in a 2-week test period (+/- 2 days) and have a scheduled visit once per week, visit 2 (V2) and visit 3 (V3). V3 will also terminate the 2-week study period unless a situation occurs where a subject terminates earlier than expected.

Withdrawn subjects must be encouraged to complete the Termination visit V3, regardless of the reason for withdrawal.

If dressing change is needed due to a clinical need between the weekly scheduled study site visits, additional visits can be performed. See section 7.2 for Dressing changes between study site visits.

If visits are needed due to circumstances related to a specific issue, an unscheduled visit can be performed. See section 7.3 for Unscheduled visits.

If the wound is evaluated by PI or delegate to be healed before or at the termination visit V3 subjects will be terminated according to termination – Wound healed. See section 7.4 Wound healed.

[figure not shown]
[figure not shown]

Figure 1: Study design CP357

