6.4. Subject withdrawal criteria

The subject is allowed to withdraw from the investigation at any time for whatever reason without any consequences for their future treatment outside the clinical investigation. The PI may withdraw a subject from the investigation at any time if they judge it to be the subject's interest.

The PI must withdraw a subject from the investigation due to:

- Noncompliance with the CIP impacting the scientific integrity of the investigation.
- If subject's safety and wellbeing is compromised by further participation.
- Subjects lost to follow-up. At least three documented attempts will be made to verify subjects lost to follow-up.

Withdrawn subjects will not be replaced by new subjects.

A subject who is withdrawn from the investigation, for any reason, will be encouraged to contact the PI if problem arises, that the subject believes are related to the clinical investigation. Subject who has not experienced any adverse events, will not be followed up. For subjects who experience adverse events see section 18.1.

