10.1. Definition of analysis populations

Intention to Treat (ITT) and Safety populations will be defined at a formal data review meeting before database lock. As a minimum, the data manager, the clinical manager, and the statistician will be involved in the classification of subjects.

The Safety population will constitute by subjects who have given informed consent. Due to the design, the ITT population is identical to the safety population.

The full analysis set (FAS) will be constituted by all subjects with valid informed consent who have been exposed to the Test Product, with information on at least either primary or secondary endpoints.

All statistical analysis will be based upon the FAS population whereas adverse events and Device deficiencies will be assessed based on the safety/ITT population. Invalid individual data points may be omitted from analysis even though the corresponding subject is part of the FAS population. Any exclusion of data points will be documented.

A formal per protocol (PP) population will be performed for the primary, secondary and exploratory endpoints. Considering the data obtained it might also be considered to make additional explorative analyses based on a subset of the ITT population.

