10.3. Analysis of primary endpoint

The primary endpoint proportion of wounds healed will be analyzed using a binomial proportion test.

The purpose of the primary analysis is to show non-inferiority to the performance of the similar product Aquacel Ag (a silver containing gelling fiber) on proportion of wounds healed, 77 %, with a non-inferiority margin of 20 %. (1)

Since the performance of Aquacel Ag is a fixed proportion, this is equivalent to testing whether the performance of Biatain Fiber Ag is superior to $77 - 20 = 57$ %.

Let the null hypothesis and the alternative hypothesis be defined as:

- $H_0: \mu_{\text{Biatain Fiber Ag}} \leq 57$ % wounds healed
- $H_1: \mu_{\text{Biatain Fiber Ag}} > 57$ % wounds healed

Where Non-inferiority will be demonstrated if H_0 is rejected.

This will be done using the proc freq procedure with a binomial test and if the lower limit of the 95 % confidence interval is above 57 % H_0 is rejected, and the success criteria fulfilled.

Furthermore, as a conservative estimate, a sensitivity analysis will be performed on the primary endpoint, where patients lost to follow-up, or otherwise missing information, will be considered not healed in regards to their wound.

The exploratory endpoints will be analysed descriptively and presented with confidence intervals.

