10.5. Level of significance and power

The study is designed with a power of 80 % and testing of the primary analysis will be done using a one-sided 0.025 significance level. No other statistical test as pre-planned.

11. Data management

Data management and the final statistical analyses of all measurements described in this protocol are carried out by Clinical Strategies, Coloplast A/S.

Data will be collected through an electronic data capturing (EDC) system on electronic Case Report Form (eCRF), a secure, internet-based case report form. This system will be used to record all subject information collected in the investigation for secure data tracking and centralised data monitoring ("remote monitoring") done by monitors, as defined in the monitoring section.

The system is designed to be compliant with the FDA requirements of 21 CFR part 11. It is a validated data management system allowing only qualified and trained personnel to enter the system. The system has full audit trail and electronic signature.

The data management system has restricted role-based access control. The principal investigator or delegate must be trained in the system prior to getting access. The sponsor will be responsible for training the investigator or delegate, in completion of the eCRF. The training is web-based and must be completed before access to the investigation is granted. Training will be documented in the data management system. The data manager will also demonstrate the system on a virtual meeting. Only the principal investigator, or delegate, will be authorised to enter data in the eCRF.

The monitor, using his/her personal login information shall verify all critical data points against the source documents and issue electronic queries for the authorised clinical site personnel to respond, as defined in the monitoring section.

A critical quality control will be performed by the sponsor's data management team and queries issued where needed. Such queries must be resolved by the site personnel.

The principal investigator, using his/her personal login information, shall sign each eCRF.

Automated, real-time access to the data enable control on study compliance and safety assessments.

A full audit trail ensures, that each user's (site personnel, monitor, sponsor, data manager) access to and actions in the system is tracked.

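### Healing recorded at V3 after the test product was stopped counts as a success, and the conservative sensitivity analysis in section 10.3 does not change that

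*Combined protocol and SAP*

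**What the plan says.** On withdrawal, section 6.4 states: "The PI may withdraw a subject from the investigation at any time". Section 5.1 adds: "Withdrawn subjects must be encouraged to complete the Termination visit V3, regardless of the reason for withdrawal". Sections 7.1 and 7.5 list a yes/no item for wound healed at V2, at V3 and at the wound-healed termination visit. Section 6.4 also says that withdrawn subjects who had no adverse event are not followed up, which does not sit with section 5.1.

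The primary endpoint (sections 5.2 and 5.4) is re-epithelialisation of at least 95% within 14 days, with a window of 2 days either side. No condition is placed on the treatment in use when the wound closed.

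Section 10.1 bases all statistical analysis on the FAS: consented subjects "who have been exposed to the Test Product, with information on at least either primary or secondary endpoints". It also plans a per-protocol analysis of the primary endpoint and allows invalid data points to be left out. It gives no membership rule for the first and no definition of invalid for the second.

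Section 10.3 sets the comparison against a published result for a similar dressing, "on proportion of wounds healed, 77 %, with a non-inferiority margin of 20" points, and success is declared "if the lower limit of the 95 % confidence interval is above 57" per cent. Its one sensitivity analysis, offered as a conservative estimate, is that "patients lost to follow-up, or otherwise missing information, will be considered not healed".

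**The concern.** A subject may be withdrawn for an adverse effect or a poor response, receive another dressing or surgical treatment, and then be seen at V3 with a closed wound. That outcome is observed, not missing. The subject was exposed and has endpoint information, so belongs to the FAS and counts as healed. The sensitivity analysis does not touch the result.

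In a randomised comparison, counting outcomes whatever treatment followed applies to both arms. Here there is one arm and a fixed threshold. Compared with counting such subjects as not healed, crediting their healing to the product can only raise the success count.

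The plan already cares about attribution: section 5.4 records antibiotic and antiseptic use so that an antimicrobial effect can be ascribed to the dressing. Replacing the dressing bears on attribution more directly, yet has no rule. At stake is whether the one check labelled conservative really is so, in a study meant to support effectiveness of this product for the CE mark.

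**Working it through.** **The plan's own figure.** Inputs from sections 10.3 to 10.5: reference 77%, margin 20 points, so threshold 57%; "testing of the primary analysis will be done using a one-sided 0.025 significance level"; power 80%; Z test with null variance.

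n = [(1.960 × √(0.57 × 0.43) + 0.842 × √(0.77 × 0.23)) / 0.20]² = 43.86, so 44, with power 0.801. This matches section 10.4. Dividing by 0.9 for dropout gives 44 / 0.9 = 48.9, so 49; the plan enrols 50. The sample size is not in question here.

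**Success rule in counts.** Section 10.3 does not name the interval. With an exact (Clopper-Pearson) interval:
- n = 50: 36 healed needed; chance of success 0.021 at a true rate of 57% and 0.844 at 77%.
- n = 44: 32 healed needed; 0.023 and 0.806.

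**Assumption.** The documents give no rate of leaving the product and then healing. Let *w* be the share of subjects who leave the product before healing and *h* the share of these recorded as healed at V3. Hold healing on the product at 57% of all subjects. The rate seen by the FAS analysis is then 0.57 + *w* × *h*, and the chance of success is P(X ≥ 36) for n = 50, or P(X ≥ 32) for n = 44, at that rate.

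| Added healing (*w* × *h*) | Average number in 50 | Rate seen | Success, n = 50 | Success, n = 44 |
|---|---|---|---|---|
| 0 | 0 | 0.57 | 2.1% | 2.3% |
| 0.02 | 1 | 0.59 | 4.0% | 4.2% |
| 0.04 | 2 | 0.61 | 7.1% | 7.3% |
| 0.06 | 3 | 0.63 | 12.0% | 11.8% |
| 0.10 | 5 | 0.67 | 27.8% | 26.2% |

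The last row takes *w* = 10%, equal to the planned dropout rate, with every such subject healed. With the same *w* and n = 50, *h* = 50% gives 9.3% and *h* = 77% gives 17.6%. At the low end, *w* = 2% with *h* = 50% gives 2.9%.

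A Wald interval at n = 50 would need only 35 healed and starts from 0.042 before any off-product healing is added. That is a separate matter.

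**Which analysis would change the result for such a subject?**
- FAS primary analysis: stays healed.
- Section 10.3 sensitivity analysis: stays healed, because the outcome is present.
- Per-protocol analysis: cannot be told, since membership is not defined. If the subject is excluded, both numerator and denominator fall by one, which is less strict than counting a failure.
- Omission of invalid data points: cannot be told, since invalid is not defined. If the V3 value were removed on this ground, the sensitivity analysis would count the subject as not healed.

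**The case against.** A reader might infer that no planned analysis could take these subjects out. The documents do not support that. Section 10.1 plans a per-protocol analysis of the primary endpoint and allows invalid data to be omitted, and a withdrawn subject is an obvious candidate for either. What stands is that both routes exist; what is missing is any rule by which they would operate.

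A reader might also infer that every withdrawn subject is assessed at day 14. V3 after withdrawal is only encouraged, and section 6.4 rules out follow-up for those without adverse events. Section 5.1 can be read as asking for an exit visit at the time of withdrawal, and handover to routine care is listed at V3, which would put other treatment after the healing assessment. Against this, sections 7.1 and 7.5 place V3 at 14 days, give or take 2. The text is ambiguous. Subjects withdrawn with an adverse event are the group most clearly affected. The documents also do not separate withdrawal from the study from stopping the dressing, and they mention surgical intervention only in the definition of serious adverse events.

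The benchmark is a further point. The documents do not say whether the study behind the 77% counted healing after a change of treatment. If it did, the FAS rule compares like with like and a stricter rule would be harder than the benchmark. This is a good reason to leave the primary analysis alone. It is not a reason to call a check conservative when it leaves such healings in.

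**Conclusion.** The point holds in a limited form. As written, healing recorded at V3 after the product was stopped is a success in the FAS analysis and in its sensitivity analysis. The two provisions that might remove it have no stated rule.

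The size rests wholly on assumed numbers. With 50 evaluable subjects, an exact interval and 57% healed on product, one such subject on average takes the chance of success from 2.1% to 4.0%, already above the one-sided 0.025 level; two take it to 7.1%. It would be tempting to read the 26% to 28% cases as the expected false-success rate. They are upper bounds: they need 10% of subjects off product, all returning for V3 and all healed, and nothing in the documents makes that likely. Nor does the finding mean that the sample size of 44 is wrong; it reproduces.

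**What to change.** In section 10.3, extend the existing sensitivity analysis. In addition to missing outcomes, count as not healed any subject who, before being recorded as healed, was withdrawn from the test product, changed to another primary dressing or had surgical closure. Report the number of such subjects beside the primary result.

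At V3 and the wound-healed visit, record whether the test product was still in use. Section 7.5 lists additional wound care products at V1, V2 and unscheduled visits but not at these two. Some V3 items are blacked out and may already cover this, in which case no new item is needed. Sections 5.1 and 6.4 on the follow-up of withdrawn subjects must be reconciled.

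The cost is one sentence in the plan, a small eCRF flag and a sensitivity estimate that may be less favourable. If the 77% design rate included one or two off-product healings in 50, the chance that the extended analysis clears the threshold at n = 50 would be 0.748 (at 0.77 − 0.02 = 0.75) or 0.633 (at 0.77 − 0.04 = 0.73), against 0.844. The primary analysis, its success rule and the sample size do not change.
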